The present application is for the development and evaluation of two VR simulations (interactive VR, 360° video) applied to the context of Emergency Medicine. The aim of this pilot study is to develop two VR simulations, and to compare their effectiveness with traditional theatre-based simulations. Given the novelty of both interactive VR and 360° video simulations, our primary objective is to compare knowledge retention and application of knowledge during a paper quiz and traditional theatre-based emergency department simulations following preparation with either 360° video training or interactive VR training. The secondary objectives are to assess the usability and feasibility (resources), as well as the emotional engagement, of the above three modalities.

Methods:

Phase 1: Creation of Content: A software engineer with expertise in video-game development will be hired to develop the computer-generated emergency department in collaboration with the educators and clinicians on the team. A theatre-based trauma scenario from the current uOttawa Emergency Department curriculum will be adapted to the **VR platform**. This virtual environment will allow a team of students to manage a patient simultaneously through their avatars, from a first-person perspective. In parallel, a well-managed depiction of the same scenario will be scripted and recorded using a **360-degree HD video** camera. The recording will be made using the investigators as actors, with additional interprofessional volunteers recruited as needed. These videos will be edited and then converted to an application that can be uploaded to the Oculus® platform. Both platforms will undergo piloting for content and usability. The amount of time, money and other resources required to develop each of these scenarios will be calculated.

Phase 2: Evaluating the intervention:

Participants: 40 residents and medical students will be recruited to participate in the evaluation of the VR modules. Participants will be randomized to one of two groups (20 participants per group) – interactive VR or 360° video education. See Figure 1.

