Pre-Test: Prior to participating in one of the two educational interventions (360°-video or interactive VR), participants will complete a pre-test of their content-specific knowledge and knowledge application with respect to basic presentations to the emergency department. All participants will complete a video-recorded simulation of an emergency department case, half will complete Case A while the remaining half will complete Case B. These cases will be counter-balanced at post-test in order to account for any possible differences in case difficulty. All participants will also complete a knowledge test which will consist of approximately 20 multiple-choice questions with a mark out of 20 for a minimum score of 0 and maximum score of 20. Questions will be based on Advanced Cardiac Life Support (ACLS) guidelines and algorithms. Team performance will be recorded for subsequent scoring (see measures and analysis section below). During the traditional theatre-based simulation sessions, we will measure the learners' HR and HRV with the use of a Polar H10™ chest belt linked with a commercial capture and analysis software (EliteHRV™) program on an iPad. This will allow us to measure both arousal and stress responses, as physiological indication of the learners' emotional engagement.

Intervention: Following the pre-test, participants will either participate in the interactive VR or the 360° educational video. In each condition, the scenarios will be matched for duration, and will be followed by a debriefing session focused on the learners' comprehension of the case, their rationales for decisions, as well as closing any observed gaps in performance. UOSSC-affiliated instructors with formalized simulation and debriefing training will lead the debriefing. The learners' HR and HRV will be captured during the simulation and the debriefing sessions as a measure of engagement during the activity.

Post-Test: Two weeks after the education session, all participants will complete a post-test of their knowledge and knowledge application (matched in difficulty with pre-test), as well as lead a theatre-based simulated case. Participants who completed Case A will now complete Case B and vice versa. The sessions will be videotaped for subsequent rating of clinical and team performance. We will also capture their HR and HRV again as measures of physiological arousal and stress.

Measures and Analyses:

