This will be an equivalency study which hypothesizes that there will not be a difference in learning between 360-VR or interactive VR. The primary outcome measures for this study will be changes in knowledge and in clinical performance from pre-test to post-test. Two experienced simulation instructors will view and score the videos, blinded to the group allocation and whether the scenario is pre or post the intervention. The raters will evaluate the learners using the Ottawa GRS scale as well as a checklist of expected actions for the scenario. The raters will independently rate the videos, and their level of agreement will be calculated using an intra-class correlations coefficient. The averaged scores, as well as scores on the knowledge tests, will be submitted to separate mixed-design analyses of variance (ANOVA) with time (pre, post) as a repeated-measure and groups (interactive VR, 360° video) as a between-subject variable. Post-hoc analyses will be conducted with relevant paired or unpaired t-tests.

The secondary outcomes measures are arousal and stress responses during pre and post theatre-based simulation sessions, educational sessions, and debriefing sessions. Mean and peak HR and HRV (rMSSD, pNN50) will be submitted to separate ANOVAs, with time (pre-test, debriefing, post-test) as a repeated measure and group (interactive VR, 360° video, theatre-based) as a between-subject variable. Post-hoc analyses will be conducted with relevant paired/unpaired t-tests.

Another secondary outcome measure will be the cost-effectiveness of the education interventions, based on Levin’s cost effectiveness model⁴ applied to simulation-based education⁵. The cost categories will include equipment and materials (e.g. market price of equipment, maintenance cost), personnel costs (e.g. staff salary, volunteer time), facility costs (e.g. facility rental fee, facility maintenance), required client inputs (e.g. learner costs, opportunity costs), and other program costs (e.g. communications fees, servers for storage and retrieval of information). These will be summed into a dollar estimation for each modality, and compared using a one-way between-subject ANOVA, with group (interactive VR, 360° video) as the between variable.

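### Quiz forms are matched but not swapped between pre- and post-test, so within-group knowledge gain carries any residual form difference, while the randomised comparison is largely protected

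*Protocol*

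**What the plan says.** Under Methods, Phase 2, Pre-Test, half the participants start on Case A and half on Case B, and the stated reason for the later swap is explicit: "These cases will be counter-balanced at post-test in order to account for any possible differences in case difficulty". The Post-Test paragraph carries it out: "Participants who completed Case A will now complete Case B and vice versa".

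The quiz is handled differently. At pre-test, "All participants will also complete a knowledge test which will consist of approximately 20 multiple-choice questions with a mark out of 20". At post-test, two weeks after the education session, "all participants will complete a post-test of their knowledge and knowledge application (matched in difficulty with pre-test"). No split into two forms and no rotation is described. How the matching is to be established is not stated either.

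Measures and Analyses then says: "The primary outcome measures for this study will be changes in knowledge and in clinical performance from pre-test to post-test". Knowledge scores go into a mixed ANOVA with "time (pre, post) as a repeated-measure and groups (interactive VR, 360° video) as a between-subject variable", followed by paired or unpaired t-tests. The hypothesis is between groups: "This will be an equivalency study which hypothesizes that there will not be a difference in learning between 360-VR or interactive VR".

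**The concern.** Two primary measures in one design get different protection against the same threat. For the simulation, the protocol allows that two cases may differ in difficulty and designs the difference out. For the quiz, it asserts equality. If everyone takes one form first and the other second, form and time are the same variable, and no model fitted afterwards can separate them. Allocation of forms has to be settled before the first pre-test, so an analysis plan cannot repair it later.

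What is at stake is the statement that participants gained knowledge. Change in knowledge is a named primary outcome, time is a factor in the model, and paired tests are foreseen. Should the two arms look alike, as hypothesised, the pre-to-post gain is the only knowledge result left to suggest that either arm learned anything, and an easier post-test form could produce it.

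**Working it through.** **Inputs from the protocol.** 40 participants, 20 per arm (Methods, Phase 2, Participants); quiz scored 0 to 20 (Pre-Test); time-by-group mixed ANOVA with paired or unpaired t-tests (Measures and Analyses). The protocol gives no derivation of the 40, no quiz SD, no pre-post correlation and no expected baseline score, so there is no stated figure to reproduce.

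**Assumptions.** Quiz SD 3 marks (range 2 to 4), pre-post correlation r = 0.5 (0.6 as a check), two-sided 5% level, and a post-test form easier by d marks for everyone.

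**Step 1: where d goes.** Let the true gain in arm g be G_g.
- Expected observed change in arm g: G_g + d. The time effect and each paired comparison are off by exactly d.
- Group-by-time contrast: (G_1 + d) − (G_2 + d) = G_1 − G_2. Here d cancels.

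**Step 2: size for the time effect with no learning.** SD of change = SD × √(2(1 − r)). Noncentrality = d / (SD of change / √40), referred to a noncentral t with 39 degrees of freedom.

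| d (marks) | SD | SD of change (r = 0.5) | Noncentrality | Significant time effect |
|---|---|---|---|---|
| 1 | 3 | 3 × √1 = 3 | 1/(3/6.325) = 2.108 | 54% |
| 1 | 4 | 4 | 1/(4/6.325) = 1.581 | 34% |
| 1 | 2 | 2 | 1/(2/6.325) = 3.162 | 87% |
| 1.5 | 3 | 3 | 1.5/(3/6.325) = 3.162 | 87% |

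**Step 3: simulation of both tests.** 20 per arm, SD 3, r = 0.6, no gain, no arm difference, 20,000 runs, unbounded scores. The direction of the shift does not affect these two-sided rates.

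| Form shift (marks) | Time effect, fixed forms | Group-by-time, fixed forms | Bias in mean change, fixed forms | Bias in mean change, forms swapped |
|---|---|---|---|---|
| 0.5 | 21% | 5.1% | 0.5 | about 0 |
| 1 | 63% | 5.1% | 1.0 | about 0 |
| 2 | 99.5% | 4.9% | 2.0 | about 0 |

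When forms are swapped but form is left out of the model, the difference between order groups stays in the error term. The group-by-time test then becomes conservative: 3.6% at a 1-mark shift and 1.5% at 2 marks, against a nominal 5%. The form term is therefore part of the remedy.

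**Step 4: the ceiling.** Whole-number scores limited to 0–20, SD 3, r = 0.5, true gain 1 mark, true arm difference 1 mark, post-test form 1 mark easier.
- Baseline mean 10 or 12: observed arm difference about 0.99 or 0.97 with fixed forms, almost no loss.
- Baseline mean 16: about 0.80 with equal forms, 0.69 with the easier form fixed at post-test, 0.74 with forms swapped.
- No true arm difference: observed difference about 0 throughout.

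At baseline 16 most of the loss comes from the scale itself (1 − 0.80 = 0.20). The easier form adds 0.80 − 0.69 = 0.11, and swapping recovers 0.74 − 0.69 = 0.05 of that.

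**The case against.** The strongest reply is that the trial does not ask whether participants improved. The primary objective compares performance "following preparation with either 360° video training or interactive VR training", and the hypothesis concerns a difference between the two modalities. That is the group-by-time contrast, in which a common form shift cancels and the false-positive rate stays near 5%. This stands. A reader might infer that the primary knowledge outcome is wholly confounded with form difficulty. The protocol does not support that: both randomised arms sit the same quiz at each visit, and the arm comparison rests on the difference in change.

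A reader might also infer that an easier post-test pushes the trial towards its hypothesised result. That holds only if scores lie near 20, and the protocol gives no expected score. A harder post-test form would work the other way.

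Two further replies carry some weight. The protocol does name a safeguard, matching, and the percentages above apply only if matching falls short by the assumed amount; nothing in the document shows that it does. Nor does the text exclude rotation of forms; it simply describes none. Against this, the same section does not rely on assumed equality for the cases, the only piloting described is of the two VR platforms, and one mark is 5% of the scale (1/20).

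Lastly, a swap would not make the gain evidence for VR. There is no untrained arm, so practice on the quiz, the pre-test simulation, the debriefing and two weeks of other training all remain in it. This also stands, and it limits what the remedy can claim.

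**Conclusion.** The point holds for within-group change only. Followed as written, the time effect and the paired t-tests on knowledge absorb any residual form difference one for one. A 1-mark mismatch would make the time effect significant without learning in about 54% of trials, and in 34% to 87% over SDs from 4 down to 2. These figures rest on an assumed correlation of 0.5 and an assumed mismatch; the protocol supplies neither. The randomised comparison that addresses equivalence is largely safe; its only exposure shown here is near the ceiling, where swapping forms helps in part. Severity is minor: this is a nearly free improvement to the design, not a flaw that undermines the main comparison.

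**What to change.** Label the two quizzes Form X and Form Y. Within each arm, give half the participants X then Y and the other half Y then X. Balance form order against case order, which gives four combinations of 20/4 = 5 participants per arm. Include form as a factor in the knowledge model alongside time and group.

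If the forms are not rotated, the protocol should say how equal difficulty is established and limit the primary knowledge inference to the group-by-time contrast. In either case, it should say that a pre-to-post gain cannot be credited to VR alone.

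The cost is one column in the allocation list and one model term, provided the post-test is a second form, as the matching implies. The change has to be made before the first pre-test.

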The properties of VR hypothesized to result in effective learning - over lectures, passive videos or discussion groups - include those of vividness (representational richness with which information is presented to the various senses) and interactivity (the ability to actively modify an environment). Increased vividness and interactivity can lead to greater emotional, motivational and cognitive engagement with learning materials. In turn, this greater engagement can lead to more active learning (analyzing, synthesizing and evaluating information rather than passively receiving it), and thus better knowledge retention and ability to apply this knowledge for subsequent problem solving. To date however, work related to VR has been targeted towards development of the technological resources to permit realistic and immersive experiences. Significant advances have led to this technology being readily affordable and accessible. However, little research has been conducted to determine the educational effectiveness of virtual simulations. Both interactive VR and 360° video provide immersive and interactive components; however, 360° video is arguably more of a passive experience for the learner. We felt that our constructed interactive VR simulation may provide more opportunity for interactivity for the learner and encourage them to participate in more active decision-making, but may increase extraneous cognitive load for the learner given the new environment. Both interactive VR and 360° video techniques require a significant investment of time and resources, but we do not yet know whether these techniques are equivalent in terms of learning or if one significantly differs from the other. There is no evidence to suggest that one method is superior to the other, therefore we chose to do a comparison study to investigate for any significant difference between these simulation experiences.

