Outcome: After six months, we will have developed interactive, virtual educational content for training medical students and residents in emergency medicine using two different VR modalities. These modalities will be easily scalable to other programs across the Faculty of Medicine. In addition, the evaluation phase will result in data to help support decisions regarding which virtual modalities are best suited to distanced simulation, in terms of educational effectiveness (knowledge, clinical performance and emotional engagement) and required costs. The calculations of costs associated with each modality will also allow for fact-based estimations of future investments in virtual-reality education.

Budget Request: \$50,000 for 1 year

Budget Justification:

Item	Price	Total
Computer Engineer	80,000/year, for 6 mos.	\$40,000
Research Assistant	5 hrs/week for 6 mos. X \$40.hr	\$7,200
Oculus Quest headset		\$800
Insta360 ONE X camera bundle with tripod		\$600
InstaVR app VR platform	\$199 USD/month = 270 CDN x 5 mos.	\$1350
		\$49,950

Computer Engineer: A software engineer, with expertise in computer-generation of environments for virtual platforms, will be hired on a full-time basis for a period of 6 months. During this period of time, the individual will work with the team to create an interactive VR trauma bay scenario (that can subsequently be adapted to other clinical content), as well as develop the 360° video based on recordings made by the team.

Research Assistant: The research assistant will support the team in the recruitment, scheduling, data collection, and data entry and analysis elements of the project. We will contract a skilled research assistant from DIME’s Research Support Unit, at their standard rate of \$40/hr

References

¹ Cook, David A., Ryan Brydges, Stanley J. Hamstra, Benjamin Zendejas, Jason H. Szostek, Amy T. Wang, Patricia J. Erwin, and Rose Hatala. "Comparative effectiveness of technology-enhanced simulation versus other instructional methods: a systematic review and meta-analysis." *Simulation in Healthcare* 7, no. 5 (2012): 308-320.

[figure not shown]
² Drummond D, Hadchouel A, Tesnière A. Serious games for health: three steps forwards. *Adv Simul (Lond)*. 2017;2:3. Published 2017 Feb 4. doi:10.1186/s41077-017-0036-3

³ Pasquier P, Gaudry S, Tesniere A, Mignon A. New insights into virtual medical education and assessment, Serious Games, and Digital Platforms. *Bull Acad Natl Med*. 2015;199(7):1153-1164.

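### The protocol declares an equivalence hypothesis, but the only primary analyses it names test for a difference and cannot support it

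*Protocol*

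**What the plan says.** Under Measures and Analyses, the Protocol sets the hypothesis for the learning outcomes: "This will be an equivalency study which hypothesizes that there will not be a difference in learning between 360-VR or interactive VR". The next sentence names the outcomes: "The primary outcome measures for this study will be changes in knowledge and in clinical performance from pre-test to post-test". The averaged performance ratings and the knowledge scores "will be submitted to separate mixed-design analyses of variance (ANOVA) with time (pre, post) as a repeated-measure", with group as the between-subject factor. The paragraph ends: "Post-hoc analyses will be conducted with relevant paired or unpaired t-tests". No other primary analysis is named, and nothing says how a null result is to be read.

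Elsewhere the aim is worded differently:

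- The Background says that "we do not yet know whether these techniques are equivalent in terms of learning or if one significantly differs from the other", and then that "we chose to do a comparison study to investigate for any significant difference between these simulation experiences".
- The primary objective, at the end of the Background, is comparative: "our primary objective is to compare knowledge retention and application of knowledge during a paper quiz and traditional theatre-based emergency department simulations". The same paragraph calls the trial a pilot.
- The Outcome section expects that "the evaluation phase will result in data to help support decisions regarding which virtual modalities are best suited to distanced simulation".

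**The concern.** An equivalence hypothesis has to be the alternative that the data can establish, with a difference of at least some stated size as the null. Here the roles are reversed. ANOVA and t-tests start from no difference and look for evidence against it. Following the plan exactly therefore gives no valid route to its declared conclusion: a significant interaction contradicts the hypothesis, and a non-significant one leaves it open.

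The risk is that non-significance is taken as confirmation. The Background invites this by posing only two outcomes, equivalent or significantly different, with no room for an inconclusive result. Anything that adds noise makes that apparent confirmation more likely: a small sample, disagreement between raters, or a quiz that discriminates poorly. If the two trainings were wrongly declared equal in learning, the later choice between them could fall to cost alone.

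**Working it through.** **Inputs from the Protocol.** 40 participants, 20 per group (Methods, Phase 2, Participants); two time points; two groups. The protocol gives no significance level, SD, margin, pre-post correlation or dropout rate. It gives no calculation behind the 40, so there is no stated figure to reproduce.

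**Assumptions, all mine.** Two-sided 5% level; the group-by-time term is decisive; no dropout unless stated; normal scores; effects in SDs of the change score.

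**Step 1: what the named test examines.** With two groups and two time points, the group-by-time F-test is the square of the unpaired t-test on change scores, with 20 + 20 − 2 = 38 degrees of freedom. Its null hypothesis is equal mean change in the two groups, which is the declared hypothesis.

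**Step 2: how often a real difference is missed.** For a true difference of d SD, the noncentrality is d/√(2/n). At n = 20, √(2/20) = 0.316 and the critical value is 2.024. The probability of a non-significant result, from the noncentral t, is:

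| Per group | d = 0.5 | d = 0.8 |
|---|---|---|
| 20 | 66.2% | 30.7% |
| 18 | 69.2% | 35.5% |
| 16 | 72.2% | 40.9% |

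**Step 3: the same in raw-score SDs.** With equal pre and post SDs and pre-post correlation r, SD of change = SD × √(2(1 − r)). At 20 per group, non-significant:

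| r | SD of change / raw SD | raw 0.5 SD | raw 0.8 SD |
|---|---|---|---|
| 0.3 | 1.183 | 74.4% | 45.1% |
| 0.5 | 1.000 | 66.2% | 30.7% |
| 0.7 | 0.775 | 48.8% | 11.1% |
| 0.8 | 0.632 | 31.7% | 2.6% |

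**Step 4: precision.** The 95% interval half-width is 2.024 × 0.316 = 0.64 SD of change. The 90% interval, which corresponds to two one-sided 5% tests, has half-width 1.686 × 0.316 = 0.53 SD.

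**Step 5: what 20 per group could show under an equivalence test.** Power of two one-sided 5% tests at a true difference of zero, integrated over the sampling distribution of the SD:

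| Margin (SD of change) | Power, one score |
|---|---|
| 0.5 | 3% |
| 0.8 | 60% |
| 0.9 | 75% |
| 0.942 | 80% |
| 1.0 | 86% |

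The 0.942 margin equals about 1.12, 0.94, 0.73 and 0.60 raw SD at r = 0.3, 0.5, 0.7 and 0.8. A margin of 0.5 SD of change needs 70 per group for 80% power (69 by the normal approximation).

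**Step 6: more than one primary score.** If equivalence must hold on every primary score and the scores are independent, power at the 0.942 margin is 0.80² = 0.64 for two scores and 0.80³ = 0.51 for three. Joint power of 80% needs 0.80^(1/2) = 0.894 per score for two, at a margin of about 1.05 SD, and 0.80^(1/3) = 0.928 per score for three, at about 1.11 SD. Correlation between scores raises joint power: three scores correlated at 0.8 give about 0.65 at the 0.942 margin and reach 80% at about 1.05 SD.

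**The case against.** The strongest reply is that one sentence is mislabelled and the analysis is sound for its real purpose. The trial is a pilot, its primary objective is to compare, and the Background describes a search for a difference. The ANOVA serves all of that. Nothing in the document says a non-significant result will be read as equivalence, and the Outcome section describes a comparative use, jointly with cost and engagement, that estimates of a difference would serve. An equivalence criterion could also be obtained from the same model, through a confidence interval set against a margin, and a statistical analysis plan not shown might hold that margin.

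Much of this is fair. The ANOVA does fit the stated objective, the harm depends on how a null result is read, and the Outcome section is only indirect support. A missing margin is not held against the protocol. What remains is that the mislabelled sentence states the hypothesis for the primary outcomes, and the same paragraph ties it to tests that cannot support it. An analysis plan that followed this paragraph faithfully would inherit the fault; one that used an equivalence criterion would add something the paragraph does not name. Pilot status argues for a more modest claim and does not turn a null result into evidence of equivalence.

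**Conclusion.** The point holds and should be corrected before analysis. The declared hypothesis and the named primary tests do not match, and this follows from the wording alone. The size of the risk rests on the assumptions listed in the working. With 20 per group, a true difference of 0.5 SD of change would be missed about two times in three and one of 0.8 SD about three times in ten. In raw-score SDs, over correlations from 0.3 to 0.8, the ranges are 74% to 32% and 45% to 3%. The Background is loosely worded rather than opposed to Measures and Analyses, and needs only to be aligned with it.

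**What to change.** **Preferred.** In Measures and Analyses, drop the equivalence label and describe a pilot study that estimates the difference between the two trainings, consistent with the comparative primary objective. For each primary score, report the between-group difference in change with its 95% confidence interval. State that a non-significant group-by-time interaction is not evidence of equivalence. The cost is a protocol wording change and an interval from data already planned, with no extra participants. The conclusion becomes more modest.

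**Alternative, if equivalence is the real aim.** Set and justify a margin for each primary score before outcome data are seen. Claim equivalence only if the 90% interval for the difference in change lies inside the margin on every primary score. Say whether the Ottawa GRS and the checklist count as one score or two, since that fixes how many scores must pass. State the power achieved with 20 per group. This costs no participants only if margins near or above 1 SD of change can be defended; a tighter margin would need a much larger trial.

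In either case, reword the Background to match the choice and to allow for an inconclusive result.

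### The primary time-by-group ANOVA gives away precision: it omits the pre-test score as a covariate and the case order that the design creates

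*Protocol*

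**What the plan says.** The Measures and Analyses section of the protocol defines the primary outcome: "The primary outcome measures for this study will be changes in knowledge and in clinical performance from pre-test to post-test". The rater-averaged performance scores and the quiz scores then go into separate mixed ANOVAs "with time (pre, post) as a repeated-measure and groups (interactive VR, 360° video) as a between-subject variable", followed by t-tests. Time and group are the only factors named.

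The Pre-Test section sets up two simulation cases: "half will complete Case A while the remaining half will complete Case B". The Post-Test section swaps them: "Participants who completed Case A will now complete Case B and vice versa". The reason given is difficulty: "These cases will be counter-balanced at post-test in order to account for any possible differences in case difficulty". The protocol does not say whether the A/B split is made within each randomised group. The quiz is taken by everyone ("All participants will also complete a knowledge test which will consist of approximately 20 multiple-choice questions") and has no A/B form.

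The Participants paragraph gives 40 participants, 20 per group, without a calculation.

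**The concern.** The design allows for the two cases differing in difficulty, but the analysis has no term for it. Each participant's change in GRS or checklist score contains the A-B gap, with a plus or minus sign set by case order. The model treats that known component as random error. It also uses the pre-test only by subtraction, although the score is available as a covariate.

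Neither omission biases the group comparison. Both widen its reported interval. With 20 per group precision is scarce, and the protocol hypothesises no difference between the two modalities. An interval wider than the data require makes a non-significant result more likely, and such a result is easily read as support for that hypothesis. The model is stated in the protocol, so this is not a detail left open for a later analysis plan.

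**Working it through.** **Inputs from the protocol.** 20 per group; two time points; model with time and group only; cases swapped between pre-test and post-test. The sample size comes with no calculation, so there is no figure to reproduce.

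**Assumed inputs, because the protocol gives none.** Scores with SD 1 at each time; pre-post correlation rho (within case order) from 0.3 to 0.9; case gap d from 0 to 1 SD; two-sided alpha 5%; a true difference of 0.8 SD for power.

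**Step 1: what the planned test is.** With two time points, the group-by-time F equals the squared t for post minus pre, with 38 error degrees of freedom.

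**Step 2: pre-test as covariate, cases equally hard.** The change-score variance is 2(1-rho). The ANCOVA variance is 1-rho², times (1 + 1/36) for estimating the slope with 40 participants. At rho 0.5: 0.75 × 1.028 = 0.771, against 1.00.

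| rho | 0.3 | 0.5 | 0.7 | 0.9 |
|---|---|---|---|---|
| ANCOVA / change-score variance | 0.67 | 0.77 | 0.87 | 0.98 |

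**Step 3: case order omitted (GRS and checklist only).** One order adds d to the change and the other subtracts it, so d² joins the residual variance. The reported SE is inflated by √(1 + d²/(2(1-rho))). At rho 0.5, d 0.5: √1.25 = 1.118.

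| Inflation of reported SE | rho 0.3 | 0.5 | 0.7 | 0.9 |
|---|---|---|---|---|
| d = 0.25 SD | 2% | 3% | 5% | 15% |
| d = 0.5 SD | 9% | 12% | 19% | 50% |
| d = 1 SD (extreme) | 31% | 41% | 63% | 145% |

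This has one of two consequences, and they do not add up:
- **Order balanced within arm:** the gap cancels from the estimate, which is no noisier. The reported SE is too large and the test is conservative.
- **Order not balanced within arm:** the estimate itself is noisier, and the SE reports that correctly.

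**Step 4: worked example, rho 0.5, d 0.5.** The SE of the group difference is √(variance × 2/20). As planned: √(1.25 × 0.1) = 0.354. With order: √(1.00 × 0.1) = 0.316. With order and pre-test: √(0.75 × 0.1) = 0.274 before the slope cost. Simulation (20,000 trials per setting) gives:

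| | Change, as planned | Change + order | ANCOVA + order |
|---|---|---|---|
| Balanced: mean SE | 0.353 | 0.314 | 0.275 |
| Balanced: type I error | 2.9% | 5.0% | 5.0% |
| Balanced: power at 0.8 SD | 61% | 69% | 80% |
| Unbalanced: mean SE | 0.352 | 0.318 | 0.279 |
| Unbalanced: type I error | 4.9% | 5.2% | 5.2% |
| Unbalanced: power at 0.8 SD | 59% | 68% | 79% |

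95% CI half-width, balanced: 2.024 × 0.353 = 0.71 SD as planned (38 df); 2.028 × 0.275 = 0.56 SD with both terms (36 df).

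**Step 5: range.** Power at 0.8 SD, planned against ANCOVA with order, balanced:
- rho 0.3, d 0.5: 48% against about 72%
- rho 0.5, d 0: 69% against 80%
- rho 0.7, d 0.5: 80% against 92%

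At rho 0.9, d 0 the half-widths are 0.285 and 0.282 SD.

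**Step 6: adding the pre-test without order.** The pre-test then carries the case effect. With balanced order and d = 1, the variance of the estimate relative to the change score is 1.11 at rho 0.7 and about 1.8 at rho 0.9. With d = 0.5 it is still below 1 at rho 0.5 (about 0.8) and rho 0.7 (about 0.9).

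**The case against.** The strongest reply is that the outcome is defined as change, that a mixed ANOVA tests change, and that choosing change scores over ANCOVA in a randomised trial is a matter of efficiency. That is true, and it is why this is an improvement to make and not an error that invalidates the trial. The reply is weaker for case order, because the protocol gives case difficulty as its reason for counterbalancing and then leaves it out of the model.

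The size is also unknown. The largest inflations need a full 1 SD gap. The Post-Test section says that the knowledge and knowledge-application test is matched in difficulty with the pre-test; if that extends to the simulation cases, d may be small. At rho 0.7 with d 0.25, balanced, power is 87% as planned and about 92% with both terms, a modest gain. This limits the benefit without removing it.

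Two qualifications stand. Calling the planned test valid means validity as a test of a difference between independent participants. The Methods describe a team managing the interactive VR patient together, while the Background describes single learners in the 360° video, so clustering in one arm is possible and is not covered here. Also, the protocol declares an equivalence study without a margin. Better precision does not supply one, and that is a separate matter.

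Finally, balance of case order within arm may already be intended. The text does not say so.

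**Conclusion.** The concern holds. The planned group-by-time test has no systematic bias, but it reports a wider interval than the data would support. For all three scores the loss comes from subtracting the pre-test instead of adjusting for it. For the GRS and checklist, the omitted case order can add to it.

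Under the assumed ranges, baseline adjustment alone lowers the variance by 2% to 33%. With a 0.5 SD case gap, omitting order inflates the reported SE by 9% to 50%. These figures depend on a correlation, a case gap and an effect size that the protocol does not give. The benefit is negligible only where the correlation is about 0.9 and the cases are equally hard.

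**What to change.** 1. State that case order is balanced within each arm: 10 participants A-first and 10 B-first per group.
2. For the Ottawa GRS and the checklist, make the primary between-group estimate the group coefficient, with its 95% CI, from an ANCOVA of post-test score on group, pre-test score and case order. Add the two terms together: pre-test without order can lose precision when the case gap is large.
3. For the quiz, use an ANCOVA of post-test score on group and pre-test score.
4. Keep the mixed ANOVA for the pre-to-post effect, which the ANCOVA does not estimate.
5. If case order has already been assigned without balancing, use the same models; type I error stays at about 5% in the worked example.

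The cost is protocol wording and an allocation list stratified for case order. Error degrees of freedom fall from 38 to 37 (quiz) or 36 (GRS, checklist). No new data are needed. In the least favourable setting examined (rho 0.9, equally hard cases, unbalanced order) the variance is about 1.01 times that of the planned analysis.
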